4.3.2 Treatment assignment

Treatment assignment will take place only after getting patients' Informed consent and determining patient's eligibility. Each patient will be assigned a unique patient number. Once assigned, numbers for any non-evaluable or discontinued patient will not be reused.

A central randomization based on a 1:1 basis, of a pre-determined randomization schedule prepared by the data management of the CRO will provide the investigator treatment allocation to empagliflozin or placebo by fax or email. Treatment allocation and a unique randomization number will be sent by the CRO to the investigator soon after a copy of the inclusion and exclusion criteria will be fulfilled and signed by the investigator in the appropriate CRF form and sent by fax or email to the data management of the study CRO. Email address: [contact]. [contact].

Blinding

The investigators, the Sponsor, and any personnel involved in patients' assessment, monitoring and data management will be blinded to the patient assignment.

The active study drug and placebo will be packaged and labeled by Boehringer Ingelheim Company.

All study drugs blisters and tablets will appear identical to ensure blinding.

Study drugs will be dispensed by the site pharmacy, in accordance with the randomization code system and the blinded study team will have no access to study drug or placebo, or randomization information.

Emergency Identification of Study drug

In case of a medical emergency, when the study drug assignment is needed to make treatment decisions for the patient, the investigator may unblind the patient's drug assignment. The Sponsor and medical monitor should be notified of the event prior to breaking of the code, if possible. If this is not possible, the Sponsor should be notified immediately afterwards, and the patient's drug code assignment should not be revealed. The circumstances leading to the breaking of the code should be fully documented, in the investigator's study files and in the patient's source documentation. Treatment assignment should not be recorded in any study documents.

The reason for breaking the blind must be documented in the patient's CRF and in the patient's medical records.

Documentation of contact or attempted contact with the clinical research physician prior to breaking the blind must also be documented in the patient's medical records.

4.4 Study drug interruption or discontinuation

4.4.1 Discontinuation of study drug

The following events will be considered as reasons for drug discontinuation:

- Subject's request
- Intolerable grade 3/4 adverse drug reaction that is judged by the investigator to be either physically or psychologically detrimental to the patient.
- Any study drug interruption that exceeds 14 consecutive days.
- Patient's non-compliance with study procedures as evaluated by PI and/or sponsor as warranting therapy discontinuation.
- Other reasons regarded by the PI as warranting therapy discontinuation.
- Premature study termination as described below.
- Pregnancy. If a woman becomes pregnant during the treatment period of the study, she will immediately be withdrawn from the study and will be followed up until delivery.

The investigator should contact the subject either by telephone or through a personal visit or a responsible relative must be contacted to determine as completely as possible the reason for the withdrawal. A complete final evaluation at the time of the patient's withdrawal should be made with an explanation of why the patient is withdrawing. If the reason for removal of a patient from the study treatment is an adverse event or an abnormal laboratory test result, the principal specific event or test will be recorded on the case report form.

The section for "Study Completion" in the CRF must be completed for all patients. The reason for early discontinuation should be given, even if the patient refused to return for a final visit. Patients whose treatment is

discontinued prematurely due to significant adverse events (AEs) should continue to be followed until resolution of the AE, and the relevant sections of the CRF should be completed as appropriate. Patients who are discontinued due to clinically significant abnormalities in clinical laboratory results should continue to be evaluated until the abnormality resolves or is judged permanent. Patients lost to follow up should be recorded as such on the CRF. If patients refuse to return for these visits or are unable to do so, the patient should be considered off-study.

Subjects withdrawn from the study will not be replaced.

4.4.2 Study drug interruption

No study drug interruption is allowed unless for safety reasons.

4.5 Study Discontinuation

The patient or the investigator can decide to discontinue subject participation on study.

Possible reasons of premature study termination include:

- Death
- Participation in another investigational drug trial
- Loss to follow-up
- Patient withdrawal of consent
- Malfunction of CRTD/ICD.
- Clinical need to begin antiarrhythmic drug excluding beta blockers.
- Occurance of myocardial infarction.
- Sepsis as a consequence of UTI or genital infection.
- Administrative problems (of the whole study)
- Patient of investigator not compliant with study protocol.

- Occurrence of an AE which makes discontinuation desirable or necessary in the investigators' and/or the patients' opinion

In those cases, no patient follow-up will be recorded.

The section for "Study Completion" in the CRF must be completed for all patients. The reason for early discontinuation should be given, even if the patient refused to return for a final visit. Patients who discontinue prematurely due to significant adverse events (AEs) should continue to be followed until resolution of the AE, and the relevant sections of the CRF should be completed as appropriate. Patients who are discontinued due to clinically significant abnormalities in clinical laboratory results should continue to be evaluated until the abnormality resolves or is judged permanent.

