6.2 Concomitant therapy

In general, concomitant medications and therapies deemed necessary for the supportive care and safety of the patient are allowed, provided their use is documented in the patient records and on the appropriate Case Report Form. The administration of antiarrhythmic treatment other than beta blockers

is NOT permitted. Similarly, the use of other concurrent investigational drugs is not allowed. The use of any of the prohibited medications or drugs/illegal substances within the prohibited time period will be considered a protocol deviation, which must be recorded on the appropriate CRF(s) or deviation violation form. Subjects with repeated protocol deviations may be discontinued from the study at the discretion of the investigator and/or sponsor.

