7.1 PVCs Burden

The primary efficacy parameter to be assessed will be PVCs burden.

PVCs burden is defined as the PVCs percentage of all beats in a pre-specified period captured on ICD or CRTD/P device.

PVCs burden will be evaluated as a part of the device interrogation on visit 1 to assess device integrity and proper function, in visit 2 to assess patient's eligibility for the study according to in- and exclusion criteria. In visits 3 and 5 to assess for treatment efficacy.

Assessment of the PVCs will be based on PVC counters for the various ICD/CRTD/P interrogated (from Medtronic, St. Jude, Guidant – Boston Scientific, Biotronik). Monitor counter reset will be conducted on visit 1,2,3,4 and 5. The equation for calculating the PVC burden for monitoring providing the PVC number per period will be:

$$PVC\ Burden(\%) = \frac{Number\ of\ PVCs}{Average\ HR\ \left(\frac{beats}{minute}\right) * 60 * 24 * (\#days\ in\ the\ period\ assessed)}$$

For monitors providing the PVC burden per hour the calculation will be:

$$PVC\ Burden(\%) = \frac{Average\ \frac{PVC}{hour}}{Average\ Heart\ Rate\left(\frac{Beats}{Minute}\right) * 60}$$

In case of device malfunction, counter malfunction or any other cause of inability to readout the device PVC counter measurement, PVC burden will be

calculated from a 12 Lead ECG Holter for 24 hours conducted at one of the last 7 days of the period assessed and will be calculated as:

$$PVC\ Burden(\%) = \frac{Number\ of\ PVCs}{Average\ Heart\ Rate\ \left(\frac{beats}{minute}\right) * 60 * 24}$$

Monitor counter readout and resetting will be performed by an electrophysiologist technician; data will be entered into the CRF by the study coordinator after approval of the principal investigator.

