9.2 Efficacy and Safety evaluation

General

All measured variables and derived parameters will be listed individually and, if appropriate, tabulated by descriptive statistics.

For categorical variables, summary tables will be provided giving sample size, absolute and relative frequency and 95% CI (Confidence Interval) for proportions by study treatment.

For continuous variables, summary tables will be provided giving sample size, arithmetic mean, standard deviation, median, minimum and maximum and 95% CI (Confidence Interval) for means of variables by study treatment.

All tests will be two-tailed, and a p value of 5% or less will be considered statistically significant.

The data will be analyzed using the SAS ® version 9.3 (SAS Institute, Cary North Carolina).

Analysis Populations

Safety Population: will include all randomized subjects who received any study drug.

Intention-to-Treat (ITT) Population: will include all subjects included in the safety population who provided at least one post-baseline assessment for the primary endpoint.

Per-Protocol Population: will include all subjects in the ITT population who complete the study in compliance with the protocol and have no major protocol violations.

9.2.1 Efficacy analysis:

The primary endpoint is the percentage of PVCs during the 2 months of empagliflozin treatment compared with the percentage of PVC on placebo.

The two-sample T-test or Non-parametric Wilcoxon-Mann-Whitney Rank sum test for independent samples (as is appropriate) will be applied for testing the carry-over effect in the primary endpoint between the two sequences.

If no carry-over effect will be observed, then The Paired T-test or non-parametric Signed-rank test for two means (as is appropriate) will be applied for analyzing the difference in the above changes between the tested treatment and placebo.

Otherwise, if a carry-over effect will be found statistically significant, then the MMRM model (Mixed-effect model for repeated measures) will be applied for analyzing the difference in the above reduction between the tested treatment and the placebo. The model will included terms for study arm (sequence), treatment and period as fixed effects, and subject nested within study arm as a random effect. Other covariates (such as age and baseline measures) will be included if they will be found different between the groups and affecting the outcome.

Secondary Endpoints:

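### Section 4.5 stops recording follow-up at exits that may be arrhythmia-related, and the default primary test drops anyone without both periods; 128 carries no allowance for that loss

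*Combined protocol and SAP*

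**What the plan says.** **Exit and follow-up.** Section 4.5 opens with "The patient or the investigator can decide to discontinue subject participation on study" and lists possible reasons. Among them are death, myocardial infarction, "Clinical need to begin antiarrhythmic drug excluding beta blockers" and "Malfunction of CRTD/ICD". It then says "In those cases, no patient follow-up will be recorded". A few lines later the same section says "Patients who discontinue prematurely due to significant adverse events (AEs) should continue to be followed until resolution of the AE", and it keeps similar follow-up for abnormal laboratory results. Section 4.4.1 counts premature termination among its reasons and asks for a full evaluation at withdrawal, without defining its content. It also says that withdrawn subjects are not replaced.

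**Antiarrhythmic use without exit.** Section 6.2 says "The use of any of the prohibited medications or drugs/illegal substances within the prohibited time period will be considered a protocol deviation". Only repeated deviations may lead to discontinuation.

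**Measurement.** Section 7.1 takes the efficacy readings at visits 3 and 5, and says "Monitor counter reset will be conducted on visit 1,2,3,4 and 5". Its formula for devices that report a PVC total divides by the days in the period assessed. Sections 4.1.1 and 7.1 name a 24-hour Holter as backup when the device cannot be read.

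**Analysis.** Section 9.2 defines ITT as treated patients with at least one post-baseline primary assessment. Section 9.2.1 says "If no carry-over effect will be observed, then The Paired T-test or non-parametric Signed-rank test" will be used. A mixed model with sequence, treatment, period and random subject applies only if carry-over is significant. Section 9.1 names the signed-rank test and an as-treated approach, but bases its power statement on a t-test with 128 patients. Section 4.2 caps enrolment at 128.

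**The concern.** The endpoint is PVC burden, and two of the listed exits, myocardial infarction and need for an antiarrhythmic, are plausibly linked to it. Section 2.2 itself says that antiarrhythmics suppress PVCs effectively. A patient who leaves in period 1 or washout has no second value and drops out of the paired test. A patient who leaves in period 2 is in the test only if someone reads the device at exit, which no section asks for.

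The patient who starts an antiarrhythmic and stays in raises a second problem. Counters are reset only at scheduled visits, so the next reading merges days before and after the drug. That mixture cannot be separated afterwards, and no rule says how it is analysed.

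Three things are at stake. The primary comparison would rest on a subset selected after randomisation. The ITT set and the default test do not fit together, and no missing-data rule joins them. The stated power also assumes no loss at all.

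**Working it through.** **Inputs from section 9.1:** difference 10, SD of within-patient differences 40, two-sided alpha 0.05, 128 patients (64 per sequence).

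**1. The plan's own figure.** The noncentrality is 10 / (40/√n) = √n/4. With n = 128 it is 2.828, and the critical t on 126 df is 1.979. Power from the noncentral t is 80.15%, so the stated 80% reproduces. A paired t-test on 127 df gives the same to within 0.01 points. 128 is the smallest n that reaches 80%.

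**2. Fewer complete pairs, t-type test.** The documents give no loss rate; 10% and 20% are assumptions.

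| Complete pairs | Power | 95% CI half-width, t × 40/√n |
|---|---|---|
| 128 | 80.1% | 7.0 |
| 127 | 79.8% | 7.0 |
| 126 | 79.5% | 7.1 |
| 115 (128 × 0.9) | 75.7% | 7.4 |
| 102 (128 × 0.8) | 70.6% | 7.9 |

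For information only, the enrolment that would leave 128 complete pairs is 128/0.9 = 142.2, so 143, or 128/0.8 = 160.

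**3. Signed-rank test, the one named in 9.1.** Its power depends on the shape of the differences, which the documents do not give. Simulated with mean 10 and SD 40:

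| Complete pairs | Normal differences | t with 5 df, scaled to SD 40 |
|---|---|---|
| 128 | about 79% | about 87% |
| 115 | about 74% | about 84% |
| 102 | about 68% | about 79% |

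Under normality about 134 complete pairs would be needed for 80%. With the heavier tails, 128 is more than enough.

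**4. What the mixed model recovers.** Assume that every lost value is in period 2, missing at random, and that the within-patient correlation is ρ. The variance of the treatment effect relative to complete pairs alone is [(1 − ρ) × n/128 + (1 + ρ)] / 2, and the effective number of pairs is n divided by that ratio.

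| n complete | ρ | Ratio | Effective pairs | Power |
|---|---|---|---|---|
| 115 | 0.3 | 0.964 | 119.2 | 77% |
| 115 | 0.5 | 0.975 | 118.0 | 77% |
| 115 | 0.7 | 0.985 | 116.8 | 76% |
| 102 | 0.3 | 0.929 | 109.8 | 74% |
| 102 | 0.5 | 0.949 | 107.5 | 73% |
| 102 | 0.7 | 0.970 | 105.2 | 72% |

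Against 75.7% and 70.6%, the gain is roughly 1 to 3 points. The case for the model is mainly that it gives ITT patients with one period a defined place in the analysis.

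**5. Bias.** No exit rate, exit reason mix or outcome after exit is given, so neither size nor direction can be calculated.

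**The case against.** **A reader might infer that the plan rules out a PVC reading at exit.** It does not. The evaluation at withdrawal in 4.4.1 applies to premature termination, and 4.5 itself refers to a final visit. The end-of-study visit includes device interrogation. A patient leaving in period 2 could therefore have a part-period reading and enter the paired test. The documents are silent on an exit reading; they do not exclude it. Nor does 4.5 make exit automatic after an infarction or an antiarrhythmic: the reasons are listed as possible ones.

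**A reader might infer that 80% power is lost with the first dropout, or is available only with a t-test.** Neither follows. At 127 or 126 pairs power still rounds to 80%, and the normal approximation needs only 126. The signed-rank test falls slightly short if differences are normal but exceeds 80% if they have heavier tails.

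**The SD may matter more than attrition.** Section 9.1 gives 40 both as the SD of measured values and as the SD of differences. If it belongs to the values, the SD of differences is 40 × √(2(1 − ρ)): 47.3 at ρ = 0.3 and 31.0 at ρ = 0.7. Power at 128 pairs is then 66% or 95%. This is a fair point and should be settled separately. It does not repair the missing rule for one-period patients.

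**The Per-Protocol set may handle antiarrhythmic use.** Partly. It excludes major violations, but 6.2 does not say whether such use is major, and the set does nothing for the ITT analysis.

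**The remedy has limits.** The mixed model assumes missing at random while the worry is outcome-related exit, and shortened periods may themselves end because of an arrhythmic event. Both stand, and they are why the fix includes sensitivity analyses.

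**Conclusion.** The point holds in this form. The plan specifies no PVC reading at a section 4.5 exit, and its default primary test discards patients without both period values although its ITT set includes them. The model that could use them is held back for significant carry-over. The primary result is therefore one for patients read in both periods, with some exits plausibly related to arrhythmia. The documents do not support a stated size or direction of bias.

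The sample size has no allowance for loss. Under a t-type test with the plan's inputs, power is 80.1% with all 128 pairs. It is essentially unchanged after one or two losses, and is 76% and 71% at assumed losses of 10% and 20%. These figures rest on an SD of differences of 40 and approximate normality. The change is worth making because it is cheap and an exit reading cannot be obtained later; the power gain alone would not justify it.

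**What to change.** 1. **Section 4.5.** Replace the no-follow-up sentence. Patients who exit and still consent have the device read and the counter reset at exit where feasible, without delaying care. Reconcile this with the adverse-event and laboratory follow-up sentences in 4.5 and with the evaluation in 4.4.1. State the minimum length a shortened period needs to enter the main analysis, and run a sensitivity analysis without shortened periods.
2. **Section 9.2.1.** Make the mixed model already specified there the primary analysis in all ITT patients, whatever the carry-over test shows, with one-period patients contributing. Keep the signed-rank test on complete pairs as a sensitivity analysis. Use data up to the start of an antiarrhythmic in the main analysis and later readings in a sensitivity analysis; for patients who stay in, this needs a device reading at that start. Reconcile this with the as-treated wording in 9.1 and with the Per-Protocol set.
3. **Section 9.1.** Say that 80% assumes a t-type test and 128 patients with both period values. Give power at assumed losses of 10% and 20%. Quote a signed-rank figure only with its distributional assumption.
4. **Device malfunction.** Sections 4.1.1 and 7.1 answer it with a Holter; section 4.5 lists it as a reason to leave. Both can hold as written, but the passages must be reconciled.

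**Cost.** Amendment wording and a few extra device readings. The downsides are shortened periods whose length may be related to outcome, reliance on missing at random and approximate normality, and only 1 to 3 points of power regained. No added enrolment is asked for.

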4.6 Premature whole study termination

- Administrative problems e.g.: recurrent serious or severe ADR clinically evaluated by PI and/or sponsor as warranting whole study termination.
- A decision made by the sponsor and/or IRB/EC and/or local regulatory agency to terminate the study

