8.1 Adverse events

The information obtained during study visit subject questioning, review of subject's compliance record, physical examinations, vital signs measurements, blood testing, and by any other means will be evaluated in light of baseline medical data and thus provide the basis for adverse events identification and grading. The adverse events reported during the trial will be graded (see [8.1.3 below](#)), documented and assessed in light of their clinical significance and relation to investigational product. In addition, the following information regarding the AE must be obtained: start date, end date (if applicable), outcome (resolved / unresolved), and action taken (e.g. dose adjustment, therapy discontinuation, concomitant medication). Adverse event monitoring will be conducted throughout subject's participation.

Information about all adverse events, whether volunteered by the patient, discovered by investigator questioning, or detected through physical examination, laboratory test or other means, will be collected and recorded on the Adverse Event Case Report Form and followed as appropriate.

Medical conditions/diseases present before starting study treatment are only considered adverse events if they worsen after starting study treatment.

Clinical events occurring before starting study treatment but after signing the informed consent form are recorded on the Medical History/Current Medical Conditions Case Report Form. Abnormal laboratory values or test results constitute adverse events only if they induce clinical signs or symptoms leading to a premature control of the abnormal value before the next scheduled laboratory test, leading to a change in study medication (e.g. dose

modification, interruption or permanent discontinuation), requires a change in concomitant therapy (e.g. addition or change in a concomitant medication, therapy or treatment) or require therapy.

Any Adverse Event occurring by the time of study completion (within four weeks of last drug intake) must be recorded on the Adverse Event CRF page.

Any adverse event term needs to be provided for each event; preferably using the short name based on the CTCAE ver. 4.0 or preferred term on the MedDRA.

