8.2 Adverse events reporting and monitoring requirements

8.2.1 General

All adverse events, serious and non-serious, will be fully documented in both source documents and CRF, and each AE will be assessed in light of its clinical significance. For each adverse event, the investigator will provide the onset, end, intensity, treatment required, outcome, seriousness and action taken with the investigational drug. The investigator will determine the relationship to the investigational drug, i.e. causality assessment, for each AE.

Events occurring prior to initiation of first dose should be recorded on the Medical History page of the CRF. Any AE occurring after initiation of the first dose and/or during any point throughout the study should be recorded on the Adverse Event page of the CRF. All adverse events occurring up to 30 days after the last dose of study drug administration should be captured in the CRF. AEs should be recorded in the CRF using the CTC AE terminology (short name). Whenever possible, diagnoses should be given when signs and symptoms are due to a common etiology.

Occurrence of any grade 4 AE must warrant clinical evaluation by the treating investigator to decide whether it is considered an SAE. If it is an SAE the investigator should report it to the sponsor within 24 hours (see [section 8.2.2 SAE Reporting](#)). Grade 4 AEs, which were not considered SAEs by the investigator, should be reviewed by the monitor who will forward them to the sponsor's medical monitor to approve that none of the AEs are SAEs.

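### Section 4.5 says nothing is followed up after a listed study exit, while section 8 requires safety recording for about four weeks without exempting early exits

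*Combined protocol and SAP*

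**What the plan says.** Section 4.5 gives eleven possible reasons for a premature end of study participation. They include death, entry into another drug trial, device malfunction, the need for an antiarrhythmic drug, myocardial infarction, urogenital sepsis, non-compliance and adverse events. Directly after the list comes "In those cases, no patient follow-up will be recorded". The next paragraph restores follow-up for two groups. For the first, "Patients who discontinue prematurely due to significant adverse events (AEs) should continue to be followed until resolution of the AE". For the second, those leaving because of a clinically significant laboratory abnormality, evaluation continues until it resolves or is judged permanent.

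Section 8 sets the safety windows:

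- 8.1: all AEs "occurring by the time of study completion (within four weeks of last drug intake) must be recorded on the Adverse Event CRF page".
- 8.2.1: "All adverse events occurring up to 30 days after the last dose of study drug administration should be captured in the CRF".
- 8.2.2: SAEs and AESIs are reported from first dose to 30 days after last dose, whatever their relation to the drug.
- 8.2.3: any SAE is reported until four weeks after participation or study drug ends. Later SAEs are reported only if attributed to the study drug.

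Section 4.4.1 adds a complete final evaluation at withdrawal. For a patient who becomes pregnant during treatment it says "she will immediately be withdrawn from the study and will be followed up until delivery".

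**The concern.** The sentence in 4.5 is general: it covers every reason listed and does not say what kind of follow-up it means. Section 8 is equally general in the other direction. No sentence ranks the two, and 4.5 does not refer the reader to section 8. Staff processing an exit would naturally turn to 4.5. The statement in 8.1 that AE monitoring runs throughout participation could reinforce the idea that collection stops at exit.

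What is at stake is the completeness and consistency of the safety data. Safety is a listed secondary endpoint (4.1.2), and 9.2.2 tabulates adverse events by treatment. Two sites facing the same exit could follow different sections. One would record a new event in the following weeks and the other would not.

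**Working it through.** The plan gives no figure to reproduce, so the check is a comparison of texts plus the length of the period in question.

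**1. Length of the section 8 windows**

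| Section | Events | Window | Early exits exempt? |
|---|---|---|---|
| 8.1 | AEs | 4 × 7 = 28 days after last intake | No |
| 8.2.1 | AEs | 30 days after last dose | No |
| 8.2.2 | SAEs, AESIs | 30 days after last dose | No |
| 8.2.3 | SAEs | 4 × 7 = 28 days after participation or study drug ends | No |

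**2. How much of the window falls after exit**

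Section 4.4.1 makes premature study termination a reason to stop study drug, so a 4.5 exit ends dosing. If the last dose is taken on the day of exit, the whole 28 or 30 days lie after exit. If it was taken d days earlier, 30 − d days remain under 8.2.1 and 8.2.2, and 28 − d under 8.1. The documents do not give d, so 30 days is the upper limit for these windows. Under 8.2.3, counted from the end of participation, the period is 28 days whatever d is.

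**3. What the two carve-outs in 4.5 leave open**

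- Death (1 reason): nothing further to record.
- Loss to follow-up and withdrawal of consent (2 reasons): recording is limited by lack of contact or permission, whatever 4.5 says.
- Myocardial infarction, urogenital sepsis, other adverse event (3 reasons): the event behind the exit is followed. A separate event that starts later, for example a renal AESI, is not covered by the carve-out.
- Another trial, device malfunction, antiarrhythmic start with no adverse event recorded, non-compliance, whole-study stop (5 reasons): there need be no causative event to follow, so the carve-outs do not apply.

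The groups add up to the list: 1 + 2 + 3 + 5 = 11. The conflict is clearest in the last group. It also touches the third group for new, unrelated events.

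**4. Other provisions**

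The final evaluation in 4.4.1 can pick up events up to the moment of withdrawal, but not after it. Pregnancy is followed to outcome under 4.4.1, 8.2.3.2 and 8.3 and is not on the 4.5 list, so it is not part of the gap.

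**5. Result**

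For a new event after exit, 4.5 read literally says not to record it, and section 8 says to record it.

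**The case against.** The strongest reply is that section 8 settles the matter. Its wording is mandatory and specific to safety, and 8.2.3 expressly runs past the end of participation. Against that stands one loose sentence in a section on patient disposition, which may have meant scheduled efficacy visits only. This largely stands. A site that omitted an SAE after exit would be disregarding an explicit duty, and the remaining exposure is probably mostly non-serious events. It does not remove the conflict, because 4.5 neither limits itself to efficacy nor points to section 8.

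A second reply is that Table 2 schedules no contact after visit 5 for completers either, so passive capture in the post-treatment window is not peculiar to early exits. That is correct. It means that clearer wording alone may change capture only modestly. But completers are not covered by an instruction to record nothing.

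A reader might also infer that a study stopped for drug harm would end safety recording, because 4.5 lists whole-study administrative problems and 4.6 gives the example "Administrative problems e.g.: recurrent serious or severe ADR clinically evaluated by PI and/or sponsor as warranting whole study termination". The documents do not support this as a finding. It carries an example from 4.6 back into 4.5. Section 4.6 has no sentence ending follow-up, and patients who leave because of a significant adverse event stay in follow-up under 4.5. A whole-study stop belongs on the list of exits without a necessary open event, and no more than that.

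**Conclusion.** The conflict between 4.5 and section 8 is real and should be corrected. Its reach is limited to new adverse events after exit, in patients who can still be contacted, at a site that follows 4.5 to the letter. The period in question is up to 28 or 30 days after last dose, and for SAEs four weeks after participation ends.

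The documents give no exit rate and no event rate after exit, so the number of events that might be missed cannot be estimated. A reader might infer that safety data will be lost, or that the loss would favour one treatment. Neither follows: section 8 remains in force, so loss is possible but not shown, and nothing in the documents bears on its direction. The primary analysis of PVC burden is not shown to be affected.

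The conclusion assumes that 4.5 means what it literally says. If the sponsor intended efficacy visits only, the correction simply states that intention.

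**What to change.** Replace the sentence in 4.5 with:

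> After study exit no further scheduled efficacy visits are recorded. AEs, SAEs, AESIs and pregnancies continue to be recorded and reported as required by section 8, as far as the patient can be contacted and has not withdrawn consent to follow-up; any SAE that becomes known is reported.

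Add no exemptions to section 8. Writing exceptions for death, loss to follow-up or withdrawn consent into it would narrow a duty that has none now. For example, an SAE learned of later in a patient recorded as lost is reportable today and should stay so. Keep the 8.2.3 rule for later SAEs attributed to study drug.

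Optionally, change the four weeks in 8.1 to the 30 days of 8.2.1. The difference is 30 − 28 = 2 days and is a wording matter only.

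The cost is one replaced sentence and, if wanted, one aligned window. No visit, call or test is added beyond what section 8 already requires. If the sponsor wants active rather than passive capture after exit, a scheduled contact would be a separate decision with its own cost.
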